9.4. Efficacy Analysis

In this First-In-Patient study anti-tumor activity is a secondary CCI objective. The main analysis populations will be based on mITT and EP (see Section [Analysis Sets](#)).

Disease response will be presented in the form of participant data listings that include, but are not limited to starting dose, disease response at each visit, and best overall response. In addition, progression date, death date, date of first response and last disease assessment date, and date of last contact will be listed.

Summary of objective response rates (ORR) and clinical benefit rate (CBR) will be provided by descriptive statistics.

Progression -free survival (PFS) is the time from start date to date of first documentation of progression, or death due to any cause. Progression is defined as the appearance of local, regional or distant disease of the same type after complete response or progression of pre-existing lesions. It does not include second primary malignancies of unrelated types.

Overall survival (OS) is the time from start date to date of death due to any cause.

Duration of Response (DOR) is defined as the duration of overall response measured from the time measurement criteria are met for complete response (CR) or partial response (PR) (whichever is first recorded) until the first date that recurrent or progressive disease is objectively documented (taking as reference for progressive disease the smallest measurements recorded since the treatment started).

Duration of Stable Disease (DOSD) is defined as stable disease measured from the start of the treatment until the criteria for progression are met, taking as reference the smallest measurements recorded since the treatment started, including the baseline measurements.

Clinical Benefit Rate (CBR) is defined as the proportion of participants who achieved anti-tumor responses of Complete Response (CR), Partial Response (PR), or Stable Disease for > 6 months (SD).

The Kaplan--Meier methods will be used to analyze all time to event endpoints. Details of these endpoint analyses methods will be included in the Statistical Analysis Plan.

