2.2. Part 2: Dose Expansion Objectives and Endpoints

Primary Objective(s): Part 2	Primary Endpoint(s): Part 2

 • To document preliminary evidence of anti-tumor activity using the Clinical Benefit rate (CBR) in participants with NSCLC. • To assess safety and tolerability of VBIR-2 in participants with NSCLC. 	
 • CBR (proportion of participants who achieve Complete Response, Partial Response or Stable Disease for > 6 months) using the Response Evaluation Criteria in Solid Tumor (RECIST) version 1.1 (Appendix 3). • Adverse Events as characterized by type, frequency, severity, timing, seriousness, and relationship to study therapy. • Laboratory abnormalities as characterized by type, frequency, severity, and timing.
Secondary Objective(s): 
 • To document preliminary evidence of anti-tumor activity in participants with NSCLC. • To evaluate the PK of tremelimumab and of sasanlimab after SC administration. • To evaluate the anti-drug antibody (ADA) response of tremelimumab and sasanlimab after SC administration with the other components. 	Secondary Endpoint(s): 
 • Objective Response Rate (ORR), Duration of Response (DOR) and Progression-Free Survival (PFS) using RECIST version 1.1 (Appendix 3). • Overall survival (OS). • Tremelimumab and sasanlimab trough concentrations after multiple dosing (C_{trough}) at various time points. • Incidence and titers of ADA and neutralizing antibodies against tremelimumab and against sasanlimab.

CCI

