7.4. Tumor Response Assessments

Tumor assessments will include all known or suspected sites of disease. Screening images may be obtained within 5 weeks of registration. Imaging obtained as part of standard of care that are performed within 28 days (-7 days) of registration may be used for screening assessment. Imaging will include (a) CT scan (computerized tomography) of the chest, abdomen and pelvis, or magnetic resonance imaging (MRI) of these same areas, and (b) bone scan, for participants with known or suspected bone metastases. Baseline brain imaging (CT or MRI) is not required, except in the case of symptomatic participants to rule out brain metastases (see Section 4).

The same imaging technique (CT scan or MRI) used to characterize lesions identified at baseline should be employed when performing on-study tumor assessments. As the intention of administration of VBIR-2 is to activate an anti-tumor immune response in the vaccine draining lymph nodes, the inguinal (limb) and axillary (arm) lymph nodes should not be used as target lesions, since injections of antigens may be given in the upper arm or thigh. It is possible that lymph nodes draining the upper arm or thigh may become enlarged following administration of the VBIR-2, and may not accurately reflect the status of underlying disease.

Anti-tumor activity will be assessed through radiological tumor assessments conducted at baseline; during treatment as specified in the [SOA](#); whenever disease progression is suspected (eg, symptomatic deterioration); and at the time of withdrawal from treatment (if not done in the previous 6 weeks).

Assessment of response will be made using RECIST version 1.1 ([Appendix 3](#)).

All participants' files and radiologic images must be available for source verification and for potential peer review. In addition, historical images (collected up to one year prior to study entry) may be requested for potential peer review.

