- Complete Response (CR): Complete disappearance of all target lesions with the exception of nodal disease. All target nodes must decrease to normal size (short axis <10 mm). All target lesions must be assessed.
- Partial Response (PR): Greater than or equal to 30% decrease under baseline of the sum of diameters of all target measurable lesions. The short diameter is used in the sum for target nodes, while the longest diameter is used in the sum for all other target lesions. All target lesions must be assessed.
- Stable: Does not qualify for CR, PR or Progression. All target lesions must be assessed. Stable can follow PR only in the rare case that the sum increases by less than 20% from the nadir, but enough that a previously documented 30% decrease no longer holds.
- Objective Progression (PD): 20% increase in the sum of diameters of target measurable lesions above the smallest sum observed (over baseline if no decrease in the sum is observed during therapy), with a minimum absolute increase of 5 mm.
- Indeterminate. Progression has not been documented, and
 - one or more target measurable lesions have not been assessed;
 - or assessment methods used were inconsistent with those used at baseline;
 - or one or more target lesions cannot be measured accurately (eg, poorly visible unless due to being too small to measure);
 - or one or more target lesions were excised or irradiated and have not reappeared or increased.

Non-target disease

- CR: Disappearance of all non-target lesions and normalization of tumor marker levels. All lymph nodes must be 'normal' in size (<10 mm short axis).
- Non-CR/Non-PD: Persistence of any non-target lesions and/or tumor marker level above the normal limits.

- PD: Unequivocal progression of pre-existing lesions. Generally the overall tumor burden must increase sufficiently to merit discontinuation of therapy. In the presence of stable disease (SD) or PR in target disease, progression due to unequivocal increase in non-target disease should be rare.
- Indeterminate: Progression has not been determined and one or more non-target sites were not assessed or assessment methods were inconsistent with those used at baseline.

New Lesions

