The appearance of any new unequivocal malignant lesion indicates PD. If a new lesion is equivocal, for example due to its small size, continued assessment will clarify the etiology. If repeat assessments confirm the lesion, then progression should be recorded on the date of the initial assessment. A lesion identified in an area not previously scanned will be considered a new lesion.

Supplemental Investigations

- If CR determination depends on a residual lesion that decreased in size but did not disappear completely, it is recommended the residual lesion be investigated with biopsy or fine needle aspirate. If no disease is identified, objective status is CR.
- If progression determination depends on a lesion with an increase possibly due to necrosis, the lesion may be investigated with biopsy or fine needle aspirate to clarify status.

Subjective progression

Participants requiring discontinuation of treatment without objective evidence of disease progression should not be reported as PD on tumor assessment CRFs. This should be indicated on the end of treatment CRF as off treatment due to Global Deterioration of Health Status. Every effort should be made to document objective progression even after discontinuation of treatment.

Table 17. Objective Response Status at each Evaluation

Target Lesions	Non-target Disease	New Lesions	Objective status
CR	CR	No	CR
CR	Non-CR/Non-PD	No	PR
CR	Indeterminate or Missing	No	PR
PR	Non-CR/Non-PD, Indeterminate, or Missing	No	PR
SD	Non-CR/Non-PD, Indeterminate, or Missing	No	Stable
Indeterminate or Missing	Non-PD	No	Indeterminate
PD	Any	Yes or No	PD
Any	PD	Yes or No	PD
Any	Any	Yes	PD

Table 18. Objective Response Status at each Evaluation for Participants with Non-Target Disease Only

Non-target Disease	New Lesions	Objective status
CR	No	CR
Non-CR/Non-PD	No	Non-CR/Non-PD
Indeterminate	No	Indeterminate
Unequivocal progression	Yes or No	PD
Any	Yes	PD

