6. ENDPOINTS AND COVARIATES

6.1. Efficacy Endpoint(s)

CCI

The main

analysis populations will be based on mITT and EP (see Section Analysis Sets).

Disease response will be presented in the form of patient data listings that include, but are not limited to starting dose, disease response at each visit, and best overall response. In addition, progression date, death date, date of first response and last disease assessment date, and date of last contact will be listed.

Summary of objective response rates will be provided by descriptive statistics. Objective tumor response, as assessed using the Response Evaluation Criteria in Solid Tumor (RECIST) version 1.1 by calculating the Objective Response Rate (ORR) and Progression-Free Survival (PFS).

Progression-free survival (PFS) is the time from start date to date of first documentation of progression, or death due to any cause. Progression is defined as the appearance of local, regional or distant disease of the same type after complete response or progression of pre-existing lesions. It does not include second primary malignancies of unrelated types.

Overall survival (OS) is the time from start date to date of death due to any cause.

Duration of Response (DOR) is defined as the duration of overall response measured from the time measurement criteria are met for complete response (CR) or partial response (PR) (whichever is first recorded) until the first date that recurrent or progressive disease is objectively documented (taking as reference for progressive disease the smallest measurements recorded since the treatment started).

Duration of Stable Disease (DOSD) is defined as stable disease measured from the start of the treatment until the criteria for progression are met, taking as reference the smallest measurements recorded since the treatment started, including the baseline measurements.

For tumor response data, the following analyses may be performed:

1. Tumor response (CR, PR, SD, PD, etc.) by cohort and visit, separately for RECIST 1.1 and irRECIST. Investigator provided tumor response will be presented by descriptive statistics (frequency and percentage).

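### The PFS text gives new lesions in participants with stable disease or partial response no route to progression, contradicting the RECIST 1.1 rule stated elsewhere in the protocol and SAP

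*Protocol*

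**What the plan says.** Protocol Section 9.4 measures PFS from the start date to the first documented progression or death. It then defines progression as "the appearance of local, regional or distant disease of the same type after complete response or progression of pre-existing lesions". The only qualifier is "It does not include second primary malignancies of unrelated types". RECIST is not mentioned in that section.

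SAP Section 6.1 carries the same definition, including the restriction to "the appearance of local, regional or distant disease of the same type after complete response" for new disease.

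Other places point to RECIST:

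- Protocol Section 2.2 lists, among the Part 2 secondary endpoints, "Progression-Free Survival (PFS) using RECIST version 1.1", with a reference to Appendix 3. The same table bases CBR, ORR and DOR on RECIST 1.1.
- Protocol Section 7.4: "Assessment of response will be made using RECIST version 1.1".
- Protocol Appendix 3, under New Lesions: "The appearance of any new unequivocal malignant lesion indicates PD". The last row of Table 17 gives PD for any new lesion, whatever the target and non-target status.
- SAP Section 6.1, in its Kaplan-Meier paragraph, takes the RECIST PFS event to be the first investigator-assessed PD or death.
- SAP Appendix 1, Table 3 dates the event at the first tumor assessment showing objective progression.

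**The concern.** The Section 9.4 sentence reads like a relapse definition for patients who have been made disease-free. Part 2 inclusion criterion 5 requires measurable disease at entry, so the new-disease limb can apply only to a participant who first reaches complete response. For everyone else, spread to a new site while known lesions hold steady has no place in the definition.

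The event rule for a time-to-event endpoint should give one date per participant. Here it gives two, depending on which section the programmer follows. Sections 9.1 and 9.3 both send the reader to Section 9.4 for efficacy definitions, so following that section would be a natural choice. Duration of stable disease, defined in the same section, runs until progression criteria are satisfied, and the only progression definition given there is the narrow one.

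**Working it through.** The plan states no PFS figure that depends on this definition, so there is nothing to reproduce. The check sets the texts side by side.

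**1. Can the sentence be read to include new lesions?** There are two ways to parse it.

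- (i) New disease after complete response; or progression of pre-existing lesions. A new lesion in stable disease or partial response meets neither limb.
- (ii) New disease after either complete response or progression of pre-existing lesions. A new lesion in stable disease or partial response is still left out. Growth of known lesions would also no longer count by itself, which cannot be intended.

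The second limb of (i) cannot be stretched to cover a new metastasis. Appendix 3 uses the same phrase for non-target disease already recorded, "PD: Unequivocal progression of pre-existing lesions", and deals with new lesions under a separate heading.

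**2. How far do Section 9.4 and Table 17 disagree?** Take each status short of PD and add a new lesion.

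- Target status: CR, PR, SD, indeterminate/missing (4).
- Non-target status: CR, non-CR/non-PD, indeterminate/missing (3).
- Combinations: 4 × 3 = 12.

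| Rule | Combinations called progression |
|---|---|
| Appendix 3, Table 17 | 12 of 12 |
| Section 9.4, parsing (i) | 1 of 12 (CR/CR only) |

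The two rules disagree in 12 − 1 = 11 of the 12. These are table cells, not proportions of participants.

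**3. Direction.** Whatever counts under parsing (i), whether growth of known lesions or new disease after complete response, is also PD under Appendix 3. The reverse is not true. The literal date is therefore the same as the RECIST date or later. If the participant stops treatment before known lesions grow, the censoring rules in SAP Table 3 could turn the event into a censored time. Both changes push the PFS curve up.

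**4. A hypothetical participant on the planned scan schedule.** Week 8: stable. Week 16: one new unequivocal lesion, known lesions unchanged. Week 24: known lesions meet the growth criterion. The PFS event falls at Week 16 under Appendix 3 and at Week 24 under Section 9.4. Scans are planned every 8 weeks to Week 32 and every 12 weeks in maintenance, so one interval is a plausible gap; an extra scan would shorten it. Section 3.1.2 encourages participants to stay on treatment for at least 24 weeks before removal for progression, so later scans can exist.

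**5. Size.** If a fraction *f* of first progressions are by new lesion alone and each is recognised a time *d* late, the progression-free proportion at time *t* rises by *f* × [S(*t* − *d*) − S(*t*)]. The documents give neither *f*, nor *d*, nor an assumed PFS curve S. No figure follows from them.

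**The case against.** The strongest reply is that RECIST governs in practice. Section 2.2 says so for PFS. Appendix 3 determines the objective status at each evaluation, so a new lesion is recorded as PD on its assessment date. Protocol 9.4 leaves the details of the time-to-event analysis to the SAP, whose event rule is first PD under RECIST or death. No text describes a second derivation that would reclassify such a PD.

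Most of this stands. It shows an unresolved contradiction, and does not show that new lesions will be ignored. It does not remove the problem, for three reasons:

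- SAP Section 6.1 states both the narrow definition and the RECIST event rule, so it conflicts with itself.
- The SAP is written for the protocol dated 16 March 2018, not for Amendment 2, which introduced the present Part 2.
- The SAP makes the Kaplan-Meier analysis optional, while protocol 9.4 requires it for all time-to-event endpoints.

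A reader might also infer that the Part 2 primary endpoint is inflated through the component of CBR that counts stable disease beyond 6 months. The documents do not support that. Section 2.2 puts CBR under RECIST 1.1, and Table 17 allows Stable only when there is no new lesion. Section 9.4 gives CBR its own paragraph, separate from the PFS one. DOR is likewise under RECIST 1.1 in Section 2.2.

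**Conclusion.** The contradiction is real under either parsing and should be removed before the analysis. Applied literally, Section 9.4 would lengthen PFS, and might lengthen duration of stable disease, which does not appear among the Part 2 endpoints in the visible text of Section 2.2. The direction is certain and the size is unknown: any number would rest on an assumed PFS median, an assumed share of new-lesion-only progressions and an assumed delay.

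The importance is moderate. PFS is secondary in a single cohort of approximately 30 participants, and no PFS hypothesis, threshold or power statement appears in the visible text. It would be too strong to conclude that PFS will be computed wrongly, or that CBR or DOR is biased.

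**What to change.** Replace the sentence in protocol Section 9.4 and SAP Section 6.1 with: *Progression is objective PD per RECIST 1.1 (Appendix 3), including any new unequivocal malignant lesion whatever the prior response; second primary malignancies of unrelated type are not progression.*

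Apply this one definition to PFS and duration of stable disease. That agrees with the RECIST 1.1 basis already stated for DOR and CBR, and with the RECIST event rule and Table 3 of the SAP, which need no change on this point.

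The cost is one sentence in each document and no additional data. PFS may look slightly less favourable than under the literal wording.

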9.5. Safety Analysis

The main analyses of DLTs will be based on the Per Protocol analysis set. Participants not meeting the criteria for inclusion in the Per Protocol Analysis set (ie, not evaluable for assessment of DLTs) will be replaced. Summaries and analyses of other safety parameters will include all participants in the Safety Analysis Set (see Section [Analysis Sets](#)).

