Protocol Activity	Screen (£28 days)	Treatment Period											Post Treatment			
		Cycle 1							Cycle 2				End of Treatment	Follow- Up (Months after EOT visit)		
Study Day		Day 1	Day 3 -6	Day 8	Day 15	Day 22	Day 29	Day 43	Day 57	Day 71	Day 85	Day 113				
Cycle Day												Day 1	Day 29	Day 57	Day 85	Day 99
Visit Window (hours)			±24 hr	±48 hr	±48 hr											
Visit Window (days)						±2	±4	±2	±4	±2	±2	±2	±2	±2	±4	±4
Study Treatment																

Abbreviations: ADA = Anti-drug antibody; Adenovirus (AdC68); EOT = End of Treatment; pDNA = Plasmid deoxyribonucleic acid, PK = Pharmacokinetics

1. Adenovirus (AdC68) will be administered intramuscularly on Cycle 1 Day 1 and Cycle 2 Day 1. Tremelimumab and sasanlimab will be administered after the adenovirus for participants assigned to receive these components.
2. Plasmid DNA (pDNA) vaccinations will be administered intramuscularly using an electroporation device on Day 29, Day 57 and Day 85 of each cycle. Tremelimumab and sasanlimab will be administered after the pDNA for participants assigned to receive these components. All pDNA vaccinations should be administered prior to administering the tremelimumab and sasanlimab.
3. Tremelimumab will be administered subcutaneously in close proximity to the vaccine injected muscle and vaccine draining lymph nodes on Day 1, Day 29, Day 57 and Day 85 of each cycle. Tremelimumab will be administered after the adenovirus or pDNA and, for participants assigned to receive sasanlimab, before the sasanlimab. Both tremelimumab injections should be administered prior to administering the sasanlimab.
4. Sasanlimab will be administered subcutaneously in close proximity to the vaccine injected muscle and vaccine draining lymph nodes on Day 1, Day 29, Day 57 and Day 85 of each cycle. Sasanlimab will be administered after the adenovirus or pDNA and after the tremelimumab.
5. Blood samples for determination of tremelimumab drug concentrations and for detection of ADA/NAb against tremelimumab will be collected as outlined in the [schedule of activities](#). Samples to be collected on dosing days are to be obtained within 6 hours prior to tremelimumab dosing.
6. For participants assigned to Cohorts 3A, 6A, and 7A only.

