3.2. DLT Definition

Severity of adverse events (AEs) will be graded according to Common Terminology Criteria for Adverse Events (CTCAE) version 5.0. For the purpose of dose escalation, any of the following AEs occurring in the first 28 days following the first AdC68 vaccination that are considered possibly related to study treatment and are not considered related to disease/progression will be classified as DLTs:

Hematologic:

- Grade ≥ 3 neutropenia lasting > 7 days.
- Febrile neutropenia (febrile neutropenia is defined as an absolute neutrophil count $< 1.0 \times 10^9/L$ with a single temperature of $> 38.3^{\circ}\text{C}$, or 101°F , or a sustained temperature of $\geq 38^{\circ}\text{C}$, or 100.4°F , for more than one hour).
- Grade ≥ 3 neutropenic infection.
- Grade ≥ 3 thrombocytopenia with \geq Grade 2 clinically significant bleeding (for bleeding events with no grading available, clinically significant bleeding is defined as requiring hospitalization or urgent medical intervention).
- Grade ≥ 3 anemia lasting more than 7 days.
- Grade ≥ 3 lymphopenia lasting more than 14 days.

Nonhematologic:

- Grade ≥ 3 AEs that are considered non-hematologic, non-hepatic major organ toxicity (excluding alopecia of any grade; Grade 3 nausea/vomiting or diarrhea < 72 hours with adequate antiemetic and other supportive care; \geq Grade 3 electrolyte abnormality that lasts < 24 to 72 hours, is not clinically complicated, and resolves spontaneously or responds to conventional medical interventions).
- Grade 3 flu-like symptoms lasting greater than 3 days with adequate treatment.
- Fever of $> 40.0^{\circ}\text{C}$, or 104.0°F , lasting for more than 3 days with adequate treatment.
- Concurrent aspartate aminotransferase (AST) or alanine aminotransferase (ALT) > 3 upper limit of normal (ULN) and total bilirubin > 2 ULN (potential Hy's law case).
- Nonhematologic laboratory abnormalities: Grade ≥ 3 laboratory abnormalities either associated with symptoms or associated with worsening of an existing condition or that suggests a new disease process or that requires additional active management (eg, discontinuation of the drug, close observation, more frequent follow-up)

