9.1. Analysis Sets

For safety evaluation, participants should have received at least one of the regimen components. For efficacy **CCI** evaluation, participants should have received at least one dose of all components administered on Cycle 1 Day 1. See Section **9.4** for definitions related to efficacy.

Participants who receive the designated investigational product of interest and have at least one post-dose drug concentration measurement will be included in the PK data analysis.

1. Safety analysis set.

The safety analysis set includes all enrolled participants who receive at least one dose of one of the components of the regimen.

2. Full analysis set.

The full analysis set includes all enrolled participants.

3. Per protocol analysis set.

The per protocol (PP) analysis set includes all enrolled participants who receive at least one dose of all regimen components administered on Cycle 1 Day 1 of study medication and who do not have major protocol deviations during the 28 days after the first vaccination.

4. Modified Intention-to-Treat analysis set.

CCI modified Intention-to-Treat (mITT), which is defined as all enrolled participants who received at least one dose of all regimen components administered on Cycle 1 Day 1.

CCI

a participant

must have at least 1 valid and determinate assay result related to the proposed analysis. Participants who have no valid and determinate assay result related to any proposed analysis will be excluded from the mITT analysis set.

CCI

5. PK analysis set.

The PK parameter analysis population is defined as all enrolled participants treated who have sufficient information to estimate at least 1 of the PK parameters of interest and who have no major protocol deviations influencing the PK assessment.

6. Immunogenicity analysis set.

The immunogenicity analysis set includes all enrolled participants who receive at least one dose of the VBIR-2 component that is the subject of the immunogenicity assessment (tremelimumab or sasanlimab).

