9.5.1. Analysis of Primary Endpoint

Dose Limiting Toxicity (DLT) is the primary endpoint of Part 1 of the study. The occurrence of DLTs observed in the dosing cohorts will govern the dose escalation as described in [Section 3.1](#). If a participant is withdrawn from study for any reason other than a DLT prior to completion of the 28-day safety observation period, a replacement participant will be assigned for the same dose as the replaced participant. The properties of the statistical methods for the analyses of DLTs are described in section [Statistical Methods and Properties](#). Adverse Events constituting DLTs will be listed per dose level. Adverse Events (AEs) will be graded by the investigator according to the CTCAE version 5.0 and coded using the Medical Dictionary for Regulatory Activities (MedDRA). The focus of AE summaries will be on Treatment Emergent-Emergent Adverse Events, those with initial onset or increasing in severity after the first dose of study treatment. The number and percentage of participants who experienced any AE, SAE, treatment related AE, and treatment related SAE will be summarized according to worst toxicity grades. The summaries will present AEs both on the entire study period by dose and by cycle.

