5.5. Other Analysis Sets

- *Per protocol analysis set.*

The per protocol (PP) analysis set includes all enrolled patients who receive at least one dose of all assigned regimen components administered Cycle 1 Day 1 of study medication and who do not have major protocol deviations during the 28 days after the first vaccination.

- *Modified Intention-to-Treat analysis set.*

CCI modified
Intention-to-Treat (mITT), which is defined as all enrolled patients who received at least one dose of all assigned regimen components administered. CCI

CCI a patient must have at least 1 valid and determinate assay result related to the proposed analysis. Patients who have no valid and determinate assay result related to any proposed analysis will be excluded from the mITT analysis set.

CCI

- *Immunogenicity analysis set.*

The immunogenicity analysis set includes all enrolled patients who receive at least one dose of the VBIR-2 component that is the subject of the immunogenicity assessment (tremelimumab or anti-PD-1 (PF-06801591)).

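### The Per Protocol rule for DLTs has no exception for participants who had a DLT, so such a participant can be dropped from the reported DLT rate and MTD estimate and replaced

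*Protocol*

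**What the plan says.** Protocol 9.5 sets the analysis population for the Part 1 primary endpoint: "The main analyses of DLTs will be based on the Per Protocol analysis set". It continues: "Participants not meeting the criteria for inclusion in the Per Protocol Analysis set (ie, not evaluable for assessment of DLTs) will be replaced". SAP 6.2 gives the same rule.

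Protocol 9.1 sets two conditions for the Per Protocol set. Participants must "receive at least one dose of all regimen components administered on Cycle 1 Day 1 of study medication", and they must be participants "who do not have major protocol deviations during the 28 days after the first vaccination". SAP 5.5 has the same two conditions but limits the first to what was assigned: "at least one dose of all assigned regimen components administered Cycle 1 Day 1 of study medication".

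Protocol 3.2 defines DLTs by "any of the following AEs occurring in the first 28 days following the first AdC68 vaccination", so the DLT window and the deviation window are the same 28 days. Footnote 1 of the study treatment schedule gives the Day 1 order: "Tremelimumab and sasanlimab will be administered after the adenovirus for participants assigned to receive these components".

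The only mention of DLTs in the replacement rules is in Protocol 9.5.1. It assigns a replacement "If a participant is withdrawn from study for any reason other than a DLT prior to completion of the 28-day safety observation period", and so leaves out those withdrawn because of a DLT.

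**The concern.** A Per Protocol set selects on what happens after dosing starts. For a toxicity endpoint, that selection can depend on the toxicity itself. A participant who reacts to AdC68 badly enough that the antibodies are withheld fails the first condition because of the event the analysis is meant to count. A participant who has a DLT and also a major deviation fails the second. In both cases the text removes the DLT from the numerator and fills the place with someone new.

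The second condition is also open to judgement after the outcome is known. SAP 5.6 and 5.6.2 have deviations classified, and population membership decided, before database closure. By then DLT status is known, because the study is open label.

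At stake are the reported Part 1 DLT rates and the MTD estimate. Protocol 9.2.2 takes the MTD from DLT-evaluable participants, and 9.5 equates not being evaluable with being outside the Per Protocol set. Protocol 3.5 describes the expansion dose as chosen on Phase 1 results.

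**Working it through.** **Inputs.** Target DLT rate 0.275, interval 0.225 to 0.325, Beta(0.5, 0.5) prior and exclusion threshold 0.95 (Protocol 9.2.1). MTD cap 32.5% (Protocol 3.3), with at least 6 DLT-evaluable participants (9.2.2). Decisions E (escalate), S (stay), D (de-escalate) and U (de-escalate and never reuse the dose) from Table 3.

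**Step 1: reproduce the plan's own table.** With x DLTs in n participants the posterior is Beta(0.5 + x, 0.5 + n − x). The unit probability mass of each interval is its posterior probability divided by its length. The largest of the three gives E, S or D, and D becomes U if P(rate > 0.275) exceeds 0.95. This reproduces 68 of the 69 cells, including every cell at n = 4, 6 and 9. The exception is 2/10: the table prints E, while the computed masses are 2.43 for under-dosing and 2.50 for proper dosing, which gives S. That cell is not used below.

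**Step 2: trace the two routes through the text.**
- *Incomplete Day 1.* The DLT window opens at the AdC68 injection and the antibodies follow. Protocol 5.4.2 has all components interrupted for Grade 3 or 4 potentially related toxicity. A qualifying event between the injections therefore puts the participant outside the Per Protocol set even though the protocol was followed. This route exists only in the four of six cohorts given tremelimumab, with or without sasanlimab. In the first two cohorts AdC68 is the only Day 1 component.
- *Major deviation.* In any cohort, a major deviation within the 28 days excludes the participant whether or not a DLT occurred.

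**Step 3: effect on the reported rate.** If one DLT participant is removed and the replacement has no DLT, x/n becomes (x − 1)/n, a fall of 1/n: 25.0 points at n = 4, 16.7 at n = 6, 11.1 at n = 9 and 8.3 at n = 12.

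| DLT participant counted | Dropped and replaced | Against the 32.5% cap |
|---|---|---|
| 2/6 = 33.3% | 1/6 = 16.7% | above, then below |
| 3/9 = 33.3% | 2/9 = 22.2% | above, then below |

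Protocol 3.3 uses 3/9 as its own example of a dose that cannot be declared the MTD. Protocol 9.2.1 states the cap as 27.5% instead. Both reversals also hold at that figure.

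**Step 4: average bias under an assumption.** Let q be the share of DLT participants who fall outside the Per Protocol set. The documents do not give it. If participants without a DLT are never excluded, a true rate p appears as p(1 − q)/(1 − pq).
- p = 32.5%, q = 5%: 0.30875/0.98375 = 31.4%.
- p = 32.5%, q = 30%: 0.2275/0.9025 = 25.2%.
- p = 40%, q = 5% to 30%: 38.8% down to 31.8%.

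**Step 5: set the competing passages side by side.**
- Protocol 3.1.1 and the heading of Table 3 count everyone treated at the dose level.
- Protocol 9.5 counts the Per Protocol set and replaces the rest.
- Protocol 9.5.1 says DLTs seen in the dosing cohorts drive escalation, and it triggers no replacement after withdrawal for a DLT.

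For a participant withdrawn for a DLT before completing Day 1 dosing, 9.5 requires a replacement and 9.5.1 does not. No passage says which prevails. Only if 9.5 also governed the decision table would 2/6 (S) be read as 1/6 (E). On that reading, 28 of the 57 printed cells with at least one DLT would move to a less conservative decision.

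**The case against.** The strongest reply is that 9.5 was never meant to govern escalation. Protocol 3.1.1, the Table 3 heading and 9.5.1 all point to everyone treated, and exempting DLT withdrawals from replacement suggests that the authors regarded those participants as informative. The event would also not be hidden. DLTs are listed per dose level, other safety summaries use the Safety set, all available safety data are reviewed before each escalation, and clinical judgement may override the model.

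The routes are narrow too. Many DLT criteria need persistence (more than 7 or 14 days for cytopenias, more than 3 days for fever or flu-like symptoms), so few events between same-day injections would qualify. Withholding doses for toxicity follows the protocol and is not in itself a deviation. The next scheduled dose is on Day 29, so little dosing falls inside the window. Finally, Part 1 is complete with 36 enrolled.

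Most of this stands, and it limits the point to the reported rate and the MTD estimate. It does not remove the gap. None of these passages changes who belongs to the Per Protocol set, and a listing does not restore a DLT to a rate. The near-Day-28 allowance in 3.1.1 covers only discontinuation for reasons other than toxicity.

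**Conclusion.** The point holds for the reported DLT rate and the MTD estimate. The rule in Protocol 9.5 and SAP 6.2, read with the set's definition, drops and replaces a participant with a DLT in two identifiable situations, and the resulting bias is downward. One such participant is enough to bring 2/6 or 3/9 under the MTD cap, provided that the replacement has no DLT.

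A reader might infer two stronger conclusions, and the documents support neither. The first is that escalation decisions were loosened, for instance from stay to escalate at n = 6. That requires 9.5 to override 3.1.1 and 9.5.1, which no passage says, so the effect on escalation is unclear. The second is that a DLT was in fact excluded in Part 1. Nothing visible shows this, and the frequency q is unknown. The figures show what the rule permits and are not an estimate of what occurred. With Part 1 finished, what remains open is the reported primary endpoint and the support it gives to the expansion dose.

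**What to change.** Define a DLT-evaluable set: all participants who received any component and either
- had a DLT within the 28-day window, or
- received all Day 1 components and completed the window, or were deemed evaluable under the existing near-Day-28 allowance in Protocol 3.1.1.

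State that a participant with a DLT is always counted and never replaced. Bring Protocol 3.1.1, 9.1, 9.5 and 9.5.1 and SAP 5.5 and 6.2 into line with this set, so that the decision table, the replacement rule, the reported rate and the MTD share one denominator. Re-run the Part 1 DLT rate and MTD table on it, with the Per Protocol result as a sensitivity analysis.

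The cost is wording in six sections and one table. If nobody with a DLT was excluded, the re-run confirms that no DLT is missing from the rate. If someone was, it corrects the primary endpoint.
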